5.7.4. Biological samples evaluation

5.7.4.1. Immunological read-outs

In case of insufficient blood sample volume to perform assays for all antibodies, the samples will be analyzed according to priority ranking provided in [Table 8](#). Testing against RIV antigens will be performed in immunogenicity subsets as defined in Section [5.2.3](#) and in [Table 9](#).

Table 8 Immunological Read-outs

Blood sampling timepoint		Group Name	Max No. subjects ^a	Component	Components priority rank
Type of contact and timepoint	Sampling timepoint				
Visit 4 (Day 151)	Post-Vacc 3	Group MenB+PCV, Placebo+PCV ^b	1000	hSBA-M13520 hSBA-NZ98/254 hSBA-M14459 hSBA-96217	1
		Groups MenB+PCV, Placebo+PCV	800	Anti-PCV13 (1,3, 4, 5, 6°, 6B, 7F, 9V, 14, 18C, 19°, 19F, 23F)	2
		Groups MenB+PCV, Placebo+ PCV	1200	DT,TT, PT, FHA, PRN, HBs, Polio, Hib ^a	See Table 9 ^a
Visit 5 (Day 301)	Pre-Vacc 4	Groups MenB+PCV Placebo+PCV ^b	1000	hSBA-M13520 hSBA-NZ98/254 hSBA-96217 hSBA-M14459	1
		Groups MenB+PCV and Placebo+PCV	1200	M,M,R, V	See Table 9 ^a
Visit 6 (Day 331)	Post-Vacc 4	Groups MenB+PCV Placebo+PCV ^b	1000	hSBA-M13520 hSBA-NZ98/254 hSBA-96217 hSBA-M14459	1
		Groups MenB+PCV Placebo+PCV	800	Anti-PCV13 (1,3, 4, 5, 6A, 6B, 7F, 9V, 14, 18C, 19A, 19F, 23F)	2
		Groups MenB+PCV and Placebo+PCV	1200	M,M,R, V	See Table 9 ^a

DT: diphtheria toxoid, TT: tetanus toxoid, FHA: filamentous hemagglutinin, PT: pertussis toxin, PRN: pertactin, HBs: Hepatitis B surface antigen, Hib: *Haemophilus influenzae* type b antigen, MMR: measles, mumps, rubella virus antigens, PCV: pneumococcal serotype antigens; V: varicella virus antigens, NA, not applicable.

* Laboratory assays

Note: As testing against pneumococcal serotypes will be performed using a multiplex assay, no ranking is applicable.

^a Testing at Visit 4, Visit 5 and Visit 6 will be performed based on immunogenicity subsets, defined in Section [5.2.3](#) and in [Table 9](#).

^b A subset (B1) of 200 subjects (120 evaluable) from Group Placebo+PCV will be tested against the 4 serogroup B strains in order to maintain the observer-blindness of the study during blood sample testing.

Table 9 Immunogenicity Subsets

Blood sampling timepoint		Group Name	Subset	Max No. subjects	Component	Components priority rank
Type of contact and timepoint	Sampling timepoint					
Visit 4 (Day 151)	Post-Vacc 3	Group MenB+PCV	A1	400	MenB	1
					PCV13	2
			A2	200	Hib	3
					Pertussis	4
		Group Placebo+PCV	A3	200	Diphtheria	5
					Tetanus	5
			B1	200	MenB	1
					Pertussis	2
Visit 5 (Day 301)	Pre-Vacc 4	Group MenB+PCV	A1	400	Polio	3
					MenB	1
			A2	200	PCV13	2
					Hib	3
			A3	200	Pertussis	4
					HepB	5
					Diphtheria	5
		Group Placebo+PCV	B1	200	Tetanus	5
					Polio	6
			A1	400	MenB	1
					Measles	2
			A2	200	Rubella	2
					Mumps	2
			A3	200	Varicella	3
					MenB	1
		Group Placebo+PCV	B1	200	Varicella	2
					Measles	3
			B2	200	Rubella	3
					Mumps	3
					MenB	1
			A1	200	Measles	2
					Rubella	2
			A2	200	Mumps	3
					Varicella	3

Blood sampling timepoint		Group Name	Subset	Max No. subjects	Component	Components priority rank
Type of contact and timepoint	Sampling timepoint					
Visit 6 (Day 331)	Post-Vacc 4	Group MenB+PCV	A1	400	MenB	1
					PCV13	2
					Measles	3
					Rubella	3
		A2	200		Mumps	3
					Varicella	4
		A3	200		MenB	1
					Varicella	2
		Group Placebo+PCV	B1	200	Measles	3
					Rubella	3
					Mumps	3
					Varicella	4
		B2	200		PCV13	1
					Varicella	2
					Measles	3
					Rubella	3
					Mumps	3

Note: The individual components and the order of testing is given below:

MenB: hSBA-M13520, hSBA-NZ98/254, hSBA-M14459, hSBA-96217.

PCV13: 1,3, 4, 5, 6A, 6B, 7F, 9V, 14, 18C, 19A, 19F, 23F – no ranking is applicable for pneumococcal serotypes as a multiplex assay will be used.

Pertussis : Pertactin, Pertussis toxin, Filamentous Hemagglutinin.

Polio: I, III, II.

5.7.5. Immunological correlates of protection

For pneumococcal conjugate vaccines for use in infants, pertussis, and rotavirus antigens no generally accepted immunological correlate of protection has been clearly identified yet.

For the following antigens in the DTPa-HBV-IPV, Hib, MMR and VV vaccines, an immunological correlate of protection has been established:

- Anti-D and anti-T concentrations ≥ 0.1 IU/mL (ELISA),
- Anti-HBS concentration ≥ 10 mIU/mL (ELISA),
- Polio ≥ 8 ED50 for types 1, 2 and 3 (neutralizing antibody assay),
- Anti-PRP concentrations ≥ 0.15 μ g/mL (ELISA),
- Anti-measles \geq threshold to be defined
- Anti-mumps \geq threshold to be defined

- Anti-rubella \geq threshold to be defined
- The immunological assay results will be communicated to the investigator as soon as they become available. For antigens for which an immunological correlate of protection has been established, the following applies.

The investigator is encouraged to share the immunological assay results for non-responders with the study subjects/subjects' parent(s)/LAR(s).

For the subjects identified as non-responders, it remains the responsibility of the investigator in charge of the subject's clinical management to determine the medical need for re-vaccination and to re-vaccinate the subjects as per local/regional practices.

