3. STUDY DESIGN OVERVIEW

Figure 1 Overview of Study Design – V72_57

**At Visit 5, either PCV13 or PCV20 will be allowed to be administered (only for subjects who have not yet reached Visit 5).

D: day; Vacc: vaccination, FU: follow-up call, RIV: routine infant vaccines (Visit 1 and Visit 2: DTPa-HBV-IPV, HRV, Hib; Visit 3: DTPa-HBV-IPV, Hib; Visit 5: MMR, VV)

Refer to Section 7.2.4 for study procedures to be considered during special circumstances.

Protocol waivers or exemptions are not allowed unless necessary for the management of immediate safety concerns. Therefore, adherence to the study design requirements, including those specified in the outline of study procedures (Section 5.5), are essential and required for study conduct. Refer to Section 7.2.4 for study procedures to be considered during special circumstances.

- **Experimental design:** Phase IIIB, observer-blind, randomized, placebo-controlled, multi-centric study with 2 parallel groups.
- **Duration of the study:**
 - Epoch 001 Primary starting at Visit 1 (Day 1) and ending at Visit 5 (Day 301).
 - Epoch 002: Secondary starting at Visit 5 (Day 301) and ending at Visit 6 (Day 331).
 - Epoch 003: Safety follow-up period starting at Visit 6 (Day 331) and ending at Visit 7 (Day 481 or Day 661). For subjects who have not yet reached the 6-month safety follow-up after the last dose at the time protocol amendment 7 takes effect, Visit 7 will take place on Day 481.
- **Primary completion Date (PCD):** Visit 7 (Day 481 or Day 661).

Refer to **glossary of terms** for the definition of PCD.

- **End of Study (EoS):** Date of the last testing/reading released of the Human Biological Samples (HBS) related to primary and secondary endpoints. Study completion must be achieved no later than 8 months after LSLV.

Refer to [glossary of terms](#) for the definition of EoS.

- **Study groups:**
 - Group MenB+PCV: rMenB+OMV NZ vaccine given concomitantly with PCV13 at 2, 4, 6, and 12 months of age. ***Either PCV13 or PCV20 is allowed to be given at 12 months of age (Visit 5) for subjects who have not reached Visit 5 at the time this protocol amendment becomes effective.*** Subjects should also receive routine infant vaccines (DtaP-HBV-IPV, HRV, Hib, MMR, VV) at applicable timepoints.

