5.3. Method of blinding

This trial is designed as an observer-blind study.

Data will be collected in an observer-blind manner. By observer-blind, it is meant that during the course of the study, the vaccines recipient and those responsible for the evaluation of any study endpoint (e.g. safety and reactogenicity) will all be unaware of which vaccine was administered. To do so, vaccine preparation and administration will be done by authorized medical personnel who will not participate in any of the study clinical evaluation assays or procedures.

Each study site is responsible for having a blinding plan. To work in an observer-blind manner, vaccine preparation and administration will be done by authorized medical personnel who will not participate in any of the study clinical evaluation assays or procedures. See the [glossary of terms](#) for definition of unblinded study staff. Two teams of study personnel will hence be set up:

- A team of unblinded personnel (responsible for the preparation and the administration of the vaccines).

- A team of blinded personnel (responsible for the clinical evaluation of the subjects including blood sampling).

Refer to the SPM for guidance on vaccine preparation and administration while maintaining the blind. The serological data, which would lead to the unblinding of the study groups, will not be available during the course of the study to any investigator or any person involved in the clinical conduct of the study (including data cleaning).

The laboratory in charge of the laboratory testing will be blinded to the treatment as well as to the subject number. In addition, a different subject code will be used for each timepoint tested. This subject coding will prevent the laboratory from linking the consecutive visits to a specific subject.

The serological data, which would lead to the unblinding of the study groups, will not be available during the course of the study to any investigator or any person involved in the clinical conduct of the study (including data cleaning).

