9.8.1. Sequence of analyses

Any analyses (including a possible interim analysis) will be conducted on data as clean as possible. All data will be analyzed at the end of the study, after availability of all immunogenicity and safety data, and presented in a final clinical study report.

If needed, an interim analysis including data up to visit 6 may be performed. Selected immunogenicity objectives and solicited safety data from all timepoints up to Visit 6 will be analyzed. The interim analysis will be performed by an independent statistician, in order to maintain the observer-blindness of the study. Study unblinding will be performed only after the final database lock. The data or the results from this interim analysis will not be used to make any decision on the continuation of this trial. Therefore no impact on the conduct or subsequent full data analysis of the trial is expected. All remaining objectives and remaining safety data will be analyzed at the end of the study and an integrated clinical report will be generated, which contains all data from the trial.

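### Protocol 5.7.5 sends assay results to investigators without limit by antigen or date, contradicting the rule in 5.3 that withholds unblinding serology during the study

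*Protocol*

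**What the plan says.** Protocol 5.7.5 (Immunological correlates of protection) lists antigens with an established correlate and then gives a general release rule: "The immunological assay results will be communicated to the investigator as soon as they become available". A second sentence follows: "For antigens for which an immunological correlate of protection has been established, the following applies". After it come the encouragement to share non-responder results with parents and the statement that re-vaccination is for the investigator to judge.

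Protocol 5.3 (Method of blinding) says the opposite, and says it twice. It describes the data as "The serological data, which would lead to the unblinding of the study groups" and rules that they "will not be available during the course of the study to any investigator or any person involved in the clinical conduct of the study".

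Protocol 9.8.1 adds: "Study unblinding will be performed only after the final database lock". Protocol Table 4 labels all three epochs observer-blind, including Epoch 003, the safety follow-up from Day 331 to Day 481 or Day 661.

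The SAP does not address release of serology to sites.

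**The concern.** A site reading 5.7.5 is told to expect assay results when they exist. A site reading 5.3 is told that it will not have them during the study. Neither section refers to the other.

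What is at stake is the blinded collection of safety data. SAEs, AESIs, medically attended AEs and AEs leading to withdrawal, counted to study end, are primary safety endpoints (Protocol Section 2). They are gathered by site interview, and the investigator judges causality (Protocol 7.2.3.2.2). SAP 5.4.1.2 plans confidence intervals for between-group differences in safety, and SAP 5.4.1.1 allows Poisson risk ratios for selected SAEs and AESIs. If staff knew the arm, differences in probing, reporting or attribution could enter those comparisons.

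The protocol already treats this serology as revealing. Under 5.2.3, 200 placebo infants (subset B1) are tested against the four MenB strains so that blindness is kept during sample testing. Sending the results to the investigator would bypass that protection.

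**Working it through.** The plan gives no figure for how much serology reveals, so there is none to reproduce. The check has three parts.

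**1. Scope of the two rules.** The release sentence in 5.7.5 names no antigen and no date. The limit to antigens with a correlate comes after it and governs only what follows, namely sharing with parents and re-vaccination. On its face, therefore, hSBA results go to the investigator. Read with its commas, the clause in 5.3 describes all serology as unblinding; read narrowly, it covers only serology that would unblind. Either reading includes hSBA, so the conflict exists under both.

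**2. Would hSBA results reveal the arm?** The inputs are the log10 GMTs in Protocol Table 19, the SDs in Table 18 and the LLOQs in Table 20. With normal log10 titers, P(titer ≥ LLOQ) = 1 − Φ((log10 LLOQ − mean)/SD). After dose 3 in MenB+PCV:

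| Strain | Mean | SD | LLOQ (protocol) | P(≥ LLOQ) |
|---|---|---|---|---|
| M13520 | 1.10501 | 0.45023 | 4 | 0.868 |
| NZ98/254 | 1.15836 | 0.51670 | 6 | 0.769 |
| M14459 | 1.26400 | 0.32193 | 5 | 0.960 |
| 96217 | 2.66753 | 0.36900 | 15 | 0.99997 |

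SAP 5.3.2 applies different limits to two strains: 6 for M13520, which gives 0.766, and 14 for 96217, which gives 0.99998. The range stays at about 77–100%.

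The documents give no placebo response rate. I assume q = 0 to 0.20 for strain 96217. Among infants with planned hSBA testing (800 MenB+PCV, 200 placebo):

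- P(MenB | ≥ LLOQ) = 800 × 0.99997 / (800 × 0.99997 + 200q). This is 1.000 at q = 0, 0.976 at q = 0.10 and 0.952 at q = 0.20.
- P(placebo | < LLOQ) = 200(1 − q) / (200(1 − q) + 800 × (1 − 0.99997)), about 0.9999 across the range.

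The testing panel is informative as well. Protocol 5.2.3 and Table 8 plan hSBA for 1000 of 1200 subjects. The remaining 1200 − 1000 = 200 are all placebo subset B2, half of that arm. Apart from missing samples, having no hSBA panel means placebo.

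**3. Could results exist before Visit 7?** On nominal days, the Visit 4 sample precedes Visit 7 by 481 − 151 = 330 or 661 − 151 = 510 days. The Visit 6 sample precedes it by 481 − 331 = 150 or 661 − 331 = 330 days. Protocol 9.8.1 also says: "If needed, an interim analysis including data up to visit 6 may be performed", and 9.8.2 says such an analysis would use final immunogenicity data. Early results are therefore possible, but no document gives an assay date.

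**The case against.** The strongest reply is that the sections can be read together. Section 5.3 says when serology is not available, so release on availability could mean after the study. A site that follows 5.3 keeps the blind. This stands as a possible reading, but 5.7.5 does not state it.

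Timing also favours the sponsor. End of Study is the last assay reading, up to 8 months after the last subject's last visit, so testing may finish after Visit 7. The interim analysis is optional and assigned to an independent statistician, and SAP 7.1 lists a single analysis of all epochs. This makes the exposure conditional; it does not remove the contradiction.

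The effect on safety is bounded. The primary safety endpoints are percentages counted whatever the judged causality, and SAP Section 6 calls them descriptive. Attribution affects only the summaries of related events, though ascertainment could still be affected. Routine-antigen values on their own would reveal little.

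A reader might infer three stronger things that the documents do not support:

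- **That parents would receive MenB results.** Parent sharing and re-vaccination are tied to antigens with a listed correlate, and MenB is not listed.
- **That re-vaccination after early results would distort later readings.** Under 5.2.3 the antigens in the primary-series routine vaccines are tested only at Visit 4, and the post-dose MMR and varicella readings are at Visit 6, the last draw.
- **That all assay results must be embargoed.** That would also hold back routine-antigen non-responder results, which bear on clinical management.

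**Conclusion.** The contradiction is real, lies in current text and is wrong as written: 5.7.5 releases without restriction what 5.3 and 9.8.1 withhold. It should not be read as showing that the blind has been or will be broken. That would require 5.7.5 to be applied literally and results to reach sites before a subject's Visit 7, and the documents establish neither.

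Under those conditions, allocation would be disclosed for most hSBA-tested infants. A 96217 titer at or above LLOQ would imply MenB+PCV with probability 95–100%, and a lower titer would imply placebo almost surely. This rests on the protocol's sample-size means and SDs, normal log10 titers and the assumed placebo response of 0–20%. The panel inference for subset B2 needs no response assumption. The exposure is in site-collected safety data; hSBA endpoints are read by a laboratory that stays blinded.

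**What to change.** Reconcile 5.7.5 with 5.3 and 9.8.1. State in 5.7.5 that hSBA results, assay-panel or subset membership, and any other allocation-revealing serology are not released to sites until after final database lock and unblinding. Subset membership needs naming because the subsets are nested in the arms: A1 to A3 are all MenB+PCV, and B1 and B2 are all Placebo+PCV.

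Separately, the sponsor should state when and in what form routine-antigen non-responder results reach sites without revealing allocation. No re-vaccination rule is proposed here.

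If results have already been produced, the sponsor should document that no allocation-revealing serology reached sites before unblinding.

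The cost is a sentence or two of protocol text and a defined release route for routine-antigen results. Sites would receive hSBA results later than a literal reading of 5.7.5 allows. Sample size, endpoints and analyses are unchanged.

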6. STUDY VACCINES AND ADMINISTRATION

6.1. Description of study vaccines

6.1.1. Study vaccines

The study vaccines' (see [glossary of terms](#)) will be provided by the Sponsor. All study participants are expected to receive these vaccines as specified by the study schedule. The study vaccines specific to this study are described below. *In exceptional circumstances, in order to avoid any inconvenience for the participant, a commercially-acquired vaccine with identical formulation and brand of that reported in the study protocol can be administered to the participant. In this case this subject will still be eligible for the Per Protocol Set.*

- GSK Biologicals' Meningococcal group-B vaccine, (rMenB+OMV NZ, *Bexsero*);
- Pneumococcal polysaccharide conjugate vaccine, (13-valent Pneumococcal Vaccine) (PCV13, *Prevnar13*) (*In order to comply with the change in the US NIP, 20-valent Pneumococcal Vaccine (PCV20, Prevnar20) will also be allowed as specified in the protocol*);
- Saline placebo vaccine.

Standardized routine infant immunizations included in this study are described below.

- GSK Biologicals' Diphtheria and Tetanus Toxoids and Acellular Pertussis Adsorbed, Hepatitis B (Recombinant) and Inactivated Poliovirus Vaccine (DTPa-HBV-IPV, *Pediarix*): a 3-dose vaccine given by IM injection at 2, 4, and 6 months of age. A single-dose prefilled syringes contains a 0.5-mL suspension for injection.
- GSK Biologicals' Rotavirus Vaccine, live, oral (HRV, *Rotarix*): a vaccine containing attenuated human strain P1AG1. HRV is a 2-dose vaccine typically given at 2 months and 4 months of age; it is available in single-dose vials of lyophilized vaccine, accompanied by a prefilled oral applicator of liquid diluent.
- GSK Biologicals' *Haemophilus influenzae* type b vaccine (Hib, *Hiberix*): a vaccine indicated for active immunization for the prevention of invasive disease caused by *Haemophilus influenzae* type b. Hib is given as a 4-dose series by IM injection; the primary series consists of one dose each at 2, 4, and 6 months of age, followed by a booster dose at 12 through 15 months of age.

- Merck's measles, mumps and rubella virus vaccine live (MMR, *M-M-R II*): a vaccine indicated for active immunization for simultaneous vaccination against measles, mumps, and rubella in individuals 12 months of age or older. Each lyophilized dose is approximately 0.5 mL after reconstitution and is administered by subcutaneous injection.
- Merck's varicella zoster virus vaccine live (VV, *Varivax*): a vaccine indicated for active immunization for the prevention of varicella in individuals 12 months of age or older. Each dose is approximately 0.5 mL after reconstitution and is administered by subcutaneous injection.

The characteristics of the study vaccines are presented in [Table 10](#).

The Quality Control Standards and Requirements for the candidate vaccine are described in separate Quality Assurance documents (e.g. release protocols, certificate of analysis) and the required approvals have been obtained.

The vaccines are labelled and packed according to applicable regulatory requirements.

Commercial vaccines are assumed to comply with the specifications given in the manufacturer's Summary of Product Characteristics.

Table 10 Study Vaccines

Treatment name	Vaccine	Formulation	Presentation	Volume to be administered*	Number of doses
Bexsero	rMenB+OMV NZ	rp936-741=50µg; rp287-953=50µg; rp961c=50µg; OMV NZ98/254=25µg; Al(OH) ₃ =1.5mg; Histidine=776µg; NaCl=3.125mg; Sucrose=10mg; water=0.5ml	Prefilled syringe (liquid)	0.5 mL	4
Prevnar13	PCV13	PS1=2.2µg CRM197; PS3=2.2µg CRM197; PS4=2.2µg CRM197; PS5=2.2µg CRM197; PS6A=2.2µg CRM197; PS6B=4.4µg CRM197; PS7F=2.2µg CRM197; PS9V=2.2µg CRM197; PS14=2.2µg CRM197; PS18C=2.2µg CRM197; PS19A=2.2µg CRM197; PS19F=2.2µg CRM197; PS23F=2.2µg CRM197; AlPO ₄ =125µg Al3+	Homogenous white suspension after shaking (in pre-filled syringe)	0.5 mL	4**

CONFIDENTIAL

205239 (MENB REC 2ND GEN-023 [V72_57])

Protocol Amendment 7 Final

Treatment name	Vaccine	Formulation	Presentation	Volume to be administered*	Number of doses
Prevnar20	PCV20	PS1(2.2 µg)^{1,2}; PS3(2.2 µg)^{1,2}; PS4(2.2 µg)^{1,2}; PS5(2.2 µg)^{1,2}; PS6A(2.2 µg)^{1,2}; PS6B(4.4 µg)^{1,2}; PS7F(2.2 µg)^{1,2}; PS8(2.2 µg)^{1,2}; PS9V(2.2 µg)^{1,2}; PS10A(2.2 µg)^{1,2}; PS11A(2.2 µg)^{1,2}; PS12F(2.2 µg)^{1,2}; PS14(2.2 µg)^{1,2}; PS15B(2.2 µg)^{1,2}; PS18C(2.2 µg)^{1,2}; PS19A(2.2 µg)^{1,2}; PS19F(2.2 µg)^{1,2}; PS22F(2.2 µg)^{1,2}; PS23F(2.2 µg)^{1,2}; PS33F(2.2 µg)^{1,2}	Suspension for injection (in pre-filled-syringe)	0.5 mL	1
Placebo	Placebo (NaCl)	NaCl=150mM	Prefilled syringe (liquid)	0.65 mL*	4
Pediarix	DTPa-HBV-IPV	DT>=30IU; TT>=40IU; PT=25µg; FHA=25µg; PRN=8µg; HbsAg=10µg; Inactivated Poliovirus type 1 (Mahoney strain)=40DU; Inactivated Poliovirus type 2 (MEF-1 strain)=8DU; Inactivated Poliovirus type 3 (Saukett strain)=32DU; Aluminium=700µg Al3+	Prefilled syringe (liquid)		3
Hiberix	Hib	PRP=10µg; TT~=25µg; Aluminium=120µg Al3+	Lyophilized cake to be reconstituted with saline diluent	0.5 mL	3
	Hib diluent (NaCl)	NaCl=150mM	Vial (liquid)		
Rotarix	HRV Lyo	HRV RIX4414 live attenuated >=10 ^{6.0} CCID ₅₀	Lyophilized vaccine in a monodose glass vial.	1 mL	2
	HRV Diluent	CaCO ₃ =60mg	Diluent for lyophilized vaccine (calcium carbonate liquid antacid) supplied separately in a prefilled oral applicator		

Treatment name	Vaccine	Formulation	Presentation	Volume to be administered*	Number of doses
M-M-R II	MMR-II	Measles>=1.000TCID50; Mumps=12.500TCID50; Rubella=1.000TCID50	Lyophilized pellet in a vial for reconstitution with water for injections	0.5 mL	1
	MMR-II diluent (Water for injection)	Water=0.5ml	vial		
Varivax	Varivax	Oka=1350pfu	Monodose vial of lyophilized vaccine	0.5 mL	1
	Varivax Diluent (Water for injection)	Water=0.5ml	vial		

Note: Refer to the SPM for the volume after reconstitution. The fourth dose of Hib vaccine will be administered as an non-study vaccine at 13 months of age.

CCID₅₀=median Cell Culture Infective Dose (quantity of virus causing infection in 50% of exposed cells)

CaCO₃: Calcium carbonate, HRV: Human Rotavirus, Hib: Haemophilus influenzae type b vaccine, DT: diphtheria toxoid, TT: tetanus Toxoid, PT: pertactin, FHA: filamentous hemagglutinin, PRN: Pertactin, HbsAg: Hepatitis B surface antigen, PRP: Polyribosyl-ribitol phosphate, MMR: measles, mumps, rubella.

* The volume of the saline syringe may be between 0.6mL and 0.8 mL. The full volume is to be injected.

** For subjects who receive PCV20 at Visit 5, only 3 doses of PCV13 will be administered.

¹conjugated to CRM₁₉₇ (51 µg);

²adsorbed on AlPO₄ (0.125 mg Al³⁺); Water for injections

